5.0 SELECTION AND WITHDRAWAL OF SUBJECTS

- 5.1 Inclusion Criteria:
 - 5.1.1 ASA I and ASA II children, aged 3-12, with interproximal decay on deciduous molars identified by radiographs. These teeth will not have previous restorations.
 - 5.1.2 Radiographic decay within enamel or extending to the dentin-enamel junction based on International Caries Classification and Management System (ICCMS)¹⁸ Categories 1 through 3 see above. Categories 1, 2 and 3 signify the extent of the "Initial Stages" of an interproximal carious lesion with radiolucency in the outer 1/2 of enamel, inner 1/2 of enamel, and outer 1/3 of dentin respectively.
 - 5.1.3 Interproximal lesions present without existing restorations, recurrent decay, or adjacent teeth with existing restorations.
 - 5.1.4 Behavior of the children should be within a Frankl 3 or 4 category²¹, indicating a "Positive" and "Definitely Positive" behavior rating, which would allow for safe and controlled execution of the proposed protocol.
- 5.2 Exclusion Criteria:
 - 5.2.1 Children who are not ASA I or ASA II.

- 5.2.2 Children who are allergic to or intolerant of SDF
- 5.2.3 Children who have known sensitivity to silver or heavy metal-ions, or have abnormal skin sensitization.
- 5.2.4 Children who have ulcerative gingivitis or stomatitis.
- 5.2.5 Carious interproximal lesions on primary molars in ICCMS Category 4, 5, or 6¹⁸, which signify the extent of the carious lesion radiographically reaching the middle 1/3 of dentin, inner 1/3 of dentin, and into the pulp respectively.
- 5.2.6 Behavior of a child within the Frankl 1 or 2 category²¹, indicating a "Definitely Negative" and "Negative" behavior, which may compromise safe application of SDF.
- 5.3 Withdrawal Criteria
 - 5.3.1 Patients can withdrawal voluntarily at any time.
 - 5.3.2 Any tooth which has progression of caries beyond ICCMS Category 3 will be withdrawn from the study. These teeth will be treated with appropriate restorative dental treatment according to the standard of care.
 - 5.3.3 Any qualifying tooth that subsequently requires a restoration or extraction due to trauma or exfoliates prematurely will be withdrawn from the study.
 - 5.3.4 Any study tooth whose adjacent tooth exfoliates before the end of this study and exposes the interproximal contact will be withdrawn from the study.

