- 3.3 Follow-Up: Recall examinations and treatment reapplication will be done at 3 months, 6 months, and 12 months after the initial visit in accordance with current American Academy of Pediatric Dentistry (AAPD) guidelines for high caries risks patients⁵. Bitewing radiographs will be taken at 6 months and 12 months. This is in accordance with the "Prescribing Dental Radiographs..." guidelines as approved by the AAPD²⁰, which state that bitewing radiographs in high risk children with dental caries are recommended every 6-12 months.
- 3.4 Providers: Residents and Attendings at the Ostrow School of Dentistry at USC, Pediatric Residency Program. All residents and attendings participating in this study will be trained and standardized on how to identify lesions of interest on radiographs, obtain consent, and apply the medications.
- 3.5 Tracking of study participants: We will count the number of participants who:
 - 1. Those who are asked to participate
 - 2. Those who consent
 - 3. Those who drop out before randomization/after randomization
 - 4. Those who withdraw by their own choice for various reasons
 - 5. Those who are lost to follow up

Note: We will only collect and store clinical data for those participants who continue throughout the duration of the project. If a participant decides to drop out of the study at any time, then we will no longer collect data from the medical record during their ongoing clinical care. We will also discard any previous data we have collected on the participants that drop out.

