10.0 CRITERIA FOR EVALUATION AND ENDPOINT DEFINITIONS

The primary outcome is arrest of interproximal caries on a primary molar, as measured by lack of change in ICCMS classification indicating caries progression on radiographic examination, (higher score indicates progression). The outcome will be evaluated at three time points: baseline, 6 months and 12 months. As the treatments cannot be made to appear similar to one another, neither the treating dentist or the patient/parent(s) will be blinded to treatment status. However, evaluation of the outcome will made by comparing time lapse (ie. comparing intial xrays vs. at 6 months vs. at 1 year) bitewing radiographs and visualizing if the carious lesion has remineralized, arrested, or progressed

11.0 SPECIAL INSTRUCTIONS:

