13.0 STATISTICAL CONSIDERATIONS

- 13.1 The proposed pilot Phase III randomized controlled clinical trial aims to determine which of the following treatments is superior in arresting dental caries among patients presenting with interproximal caries scoring RA1 RA3 on the International Caries Classification and Management System (ICCMS): (1) Fluoride varnish (FV, current standard of care, control), (2) Super floss + SDF + FV, (3) SDF + FV. We hypothesize that group 2 will have the best outcomes, as measured by no change or reversal in ICCMS classification indicating no caries progression or remineralization on radiographic examination, (higher score indicates progression) followed by group 3. As we could find no data on ICCMS-defined progression or remineralization rates for either Super Floss or fluoride, we were unable to calculate power. Instead, we provide estimates of recruitment based on feasibility. We expect to accrue approximately 20 participants, with 2 qualifying teeth per participant, in each group.
- 10% loss to follow up has increased dramatically to ~48%. Given this unexpected setback, we now need to continue recruiting participants to reach sufficient power. We originally planned to enroll 39 subjects in the study, but would now like to add 21 new participants for a total of 60 participants.

Descriptive statistics will be calculated for all demographic and clinical characteristics to assess the degree to which randomization was successful using means and standard deviations or medians and interquartile ranges for continuous variables and counts and percentages for categorical variables.

The primary analysis will be by intent-to-treat. The primary outcome is the change in ICCMS category, as assessed by radiographic evidence, from baseline to 12 months, with a planned interim analysis to evaluate the endpoint at 6 months for early indications of efficacy. We will calculate the median difference at each time point and use an individual-level model with an adjustment to the standard error to account for the clustering. First we will evaluate the association between treatment groups and the change in ICCMS score from baseline at 6 and 12 months using a cluster-adjusted chi-squared test. We will further assess

14

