the relationship between these two variables using generalized estimating equations, specifying a Poisson (or negative binomial, if overdispersed) family and a log link. We will also specify an exchangeable correlation matrix and a robust standard error.

Since the study is randomized, we do not anticipate needing to adjust for any confounders. However, should we find any differences in demographic or clinical variables at baseline, we will investigate them as potential confounders, which will be defined as those variables which alter the odds ratio by >15% when included in the model.

For those with missing data on outcomes or other covariates to be included in the model, we will consider multiple imputation methods if the amount of missing data is <10%. To assess the impact of missing data, we will compare those with missing data to those not missing data with respect to demographic and clinical variables to assess comparability. Should imputation be utilized, a sensitivity analysis will be conducted excluding those for whom data was imputed to assess the impact of imputation.

Model fit will be evaluated by inspection of residuals and influential points. As we are conducting an interim analysis, we will use a two-sided Bonferroni-corrected p-value of a=.025 for statistical significance. Finally, to assess the degree to which the two raters agree with respect to classifying the outcome of the x-rays, we will calculate and report Kappa. All statistical analyses will be done using Stata 15.0 (College Station, TX).

Power Analysis

We calculated power using a cluster-randomized design. We were unable to locate any previous studies examining the impact of these three treatments (or any two) using the same classification system as our outcome. However, we were able to obtain an estimate of 0.0 to 0.25 for the interclass correlation coefficient (ICC) (Honkala et al., 2011). Assuming the mean ICC, and assuming a clinically significant mean difference of 0.2, a standard deviation of 0.2, a covariance of cluster sizes of 0.65, two caries on average per child, and a two-sided adjusted Type I error rate of 0.025 to account for the three time points at which the data will be analyzed, we will have 80% power with 11-12 participants per group, for a total of 33-36 participants (66-72 caries). Since we anticipate significant loss-to-follow-up over the course

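### A tooth restored after reaching category 4 by 6 months has no defined 12-month score, and leaving it out would overstate arrest in each arm

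*Combined protocol and SAP*

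**What the plan says.** Section 5.3.2 (withdrawal criteria): "Any tooth which has progression of caries beyond ICCMS Category 3 will be withdrawn from the study". It continues: "These teeth will be treated with appropriate restorative dental treatment according to the standard of care". Section 7.3.4 stops study treatment once a lesion reaches category 4 and gives no scoring rule.

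Section 3.3: "Bitewing radiographs will be taken at 6 months and 12 months".

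Section 10.0: "The primary outcome is arrest of interproximal caries on a primary molar", judged by whether the ICCMS class has risen. Section 13.0: "The primary outcome is the change in ICCMS category, as assessed by radiographic evidence, from baseline to 12 months", with an interim analysis at 6 months.

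On the analysis set, Section 13.0 says: "The primary analysis will be by intent-to-treat". On missing outcomes it says: "we will consider multiple imputation methods if the amount of missing data is <10" per cent. It names no method for larger amounts. The same section reports that loss to follow-up has risen to about 48%.

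No section gives a 12-month value for a tooth withdrawn under 5.3.2. There is no carry-forward, no rule that it counts as progressed, and no composite endpoint.

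**The concern.** The withdrawal rule is triggered by the outcome itself. A lesion read as category 4 or higher on the 6-month film has failed and the failure is on record. The surface is then restored, so the 12-month film cannot supply a change score. For lesions that enter at category 3, every progression triggers the rule. A category 4 reading first made at 12 months is not affected, because that film is the endpoint.

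The primary aim in Section 2.1 is a within-arm claim: that SDF with Super Floss dependably arrests these lesions. Dropping only known failures inflates exactly that figure. The comparison between arms can also be distorted. With the rule unstated, the choice could be made after the outcomes are known.

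**Working it through.** The plan gives no figure on this point, so there is none to reproduce. Its sample size does not depend on the withdrawal rule.

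**Direction, without assumptions.** Let N be the lesions in an arm, A those arrested, and W those withdrawn at category 4 or higher by 6 months. Entry is limited to categories 1 to 3 (Section 5.1.2), so each of the W lesions has risen by at least one category and none belongs to A.

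- Withdrawn lesions counted as progressed: arrest = A/N.
- Withdrawn lesions left out: arrest = A/(N − W), which exceeds A/N whenever W and A are above zero.

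Section 13.0 expects about 20 children per arm with 2 teeth each, so N = 40:

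| W | A | A/N | A/(N − W) |
|---|---|---|---|
| 2 | 20 | 50.0% | 20/38 = 52.6% |
| 2 | 28 | 70.0% | 28/38 = 73.7% |
| 4 | 28 | 70.0% | 28/36 = 77.8% |
| 8 | 28 | 70.0% | 28/32 = 87.5% |

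The change score is biased the same way. If the true mean change is +0.2 and 10% of lesions, each at +1, are removed, the rest average (0.2 − 0.1)/0.9 = +0.11.

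**Size, under stated assumptions.** The documents give neither progression rates nor the baseline category mix. Let p be true 12-month progression, s the share of lesions entering at category 3, f the share of progression visible by 6 months, and k = s × f. Progression is taken to be equally likely at each entry category, and k to be the same in both arms. Lesions that jump from category 1 or 2 to category 4 by 6 months are ignored; including them would increase the within-arm bias. Then:

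- lesions lost = N × k × p
- observed arrest = (1 − p)/(1 − kp)

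Base case: s = 1/3, f = 0.5, k = 1/6, with p = 0.30 for varnish and 0.10 for Super Floss.

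- Varnish: 0.70/0.95 = 73.7% (true 70%); lost 40 × 1/6 × 0.30 = 2.0 lesions.
- Super Floss: 0.90/0.9833 = 91.5% (true 90%); lost 40 × 1/6 × 0.10 = 0.7 lesion.
- Difference: 17.8 points (true 20).

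Range, with s from 20% to 50% and f from 25% to 75% (k from 0.05 to 0.375):

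| k | Varnish arrest | Super Floss arrest | Difference |
|---|---|---|---|
| 0.05 | 0.70/0.985 = 71.1% | 0.90/0.995 = 90.5% | 19.4 points |
| 0.375 | 0.70/0.8875 = 78.9% | 0.90/0.9625 = 93.5% | 14.6 points |

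**Contrast between arms.** With progression a (varnish) and b (Super Floss), the observed difference is (a − b)(1 − k)/[(1 − ka)(1 − kb)]. It shrinks when a + b − kab < 1 and widens when that sum exceeds 1.

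- At 30% v 10% and k = 1/6: 0.40 − 0.005 = 0.395, so it shrinks.
- At 70% v 50%: 51.3% − 31.1% = 20.2 points at k = 0.05, and 61.5% − 40.7% = 20.9 points at k = 0.375, so it widens from 20.

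If the share of all lesions withdrawn differs between arms, the shift can be larger. With true arrest of 50% v 70% and withdrawals of 20% v 10%, the difference reads 0.70/0.90 − 0.50/0.80 = 15.3 points.

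**The case against.** **The harm is conditional.** Nothing says that withdrawn teeth leave the analysis. The analysis is labelled intent-to-treat, and Section 10.0 evaluates lesions at 6 months too, so a careful analyst might count these teeth as progressed. That is true, but the label supplies no value for a restored surface, and 5.3.2 removes the tooth from the study, not only from treatment.

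**The 6-month failure may still enter the main model.** If the generalized estimating equations use both visits, it contributes there. The text does not settle whether they do. It would not repair a 12-month estimate: the 12-month value is missing because of the 6-month result, and ordinary GEE is not generally valid in that case. A robust standard error does not remove the bias. These failures do remain visible in the 6-month analysis.

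**The base-case shift is small against sampling error.** This stands. With the plan's mean ICC of 0.125, a cluster-size variation of 0.65 read as a coefficient of variation, and 2 lesions per child, the design effect is 1 + [(0.65² + 1) × 2 − 1] × 0.125 = 1.23. At 40 lesions the standard errors are √(0.9 × 0.1 × 1.23/40) = 5.3 points for Super Floss and √(0.7 × 0.3 × 1.23/40) = 8.0 for varnish, so √(5.3² + 8.0²) = 9.6 for the difference. The base-case shifts are 1.5, 3.7 and 2.2 points. They are systematic, however, and always flatter the within-arm result. In the base case the contrast shrinks, which is conservative for the superiority hypothesis.

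**The counts assume full follow-up.** This also stands. If 48% of lesions were lost evenly before the 6-month film, 2.0 × 0.52 = 1.0 and 0.67 × 0.52 = 0.35 failures would be dropped. The percentages would not change.

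**The 10% limit might be met.** Section 3.5 discards data on participants who drop out, so missingness among those retained could fall below 10%. That is possible, but imputation would then replace an observed failure with a modelled value. Section 3.5 covers children who leave, not teeth withdrawn for progression.

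**Conclusion.** The concern holds and should be fixed. The plan withdraws a tooth because it has failed, sets the primary endpoint after that withdrawal, and does not say how the tooth is scored. If such teeth are left out, arrest is overstated in any arm with at least one of them and at least one arrested lesion; this needs no assumption.

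The size rests on assumed rates. At 30% v 10% progression, the overstatement over the range examined is 0.5 to 3.5 points for Super Floss and 1.1 to 8.9 for varnish, and a true 20-point difference reads as 14.6 to 19.4. The direction for the contrast is not fixed: at 70% v 50% it widens slightly. The likely effect is modest, but it bears on the primary aim and is easily avoided.

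**What to change.** Add to Sections 5.3.2 and 13.0, in words such as:

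> *A lesion scored category 4 or higher at any visit stops study treatment and is restored, but remains in the intent-to-treat analysis. It counts as progressed at that visit and all later ones, and its observed category is carried to 12 months.*

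Also:

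- Treat as missing only teeth lost under 5.3.3 and 5.3.4 (trauma, exfoliation, loss of the adjacent tooth).
- Keep the child's other lesions in the analysis. Section 7.3.4 speaks of the patient stopping treatment; aligning it to the tooth would be tidy.
- Report the number of teeth withdrawn under 5.3.2 by arm and visit.
- Acknowledge that, for the change score, carrying the category forward fixes a restored lesion at its last observed value. For the binary arrest outcome it adds no further assumption.

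The cost is one or two sentences and no new data, since the score is read on the film that triggers withdrawal. Reported arrest rates become slightly less favourable.

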6.0 STRATIFICATION/DESCRIPTIVE FACTORS/RANDOMIZATION SCHEME

- 6.1 We have not defined any *a priori* stratification factors.
- 6.2 Descriptive factors: Age, Gender, Race,, Date of Initial exam, Date of Recall exam/Followup, , Number of posterior caries on primary teeth that qualify for this present study, DMFS, Which interproximal surface (mesial or distal), Which primary molar, and Radiographic depth of Lesion based on ICCMS Categories (see Table 1 in Appendix).
- 6.3 Once participants have met eligibility criteria and have undergone the informed consent process (parental permission and assent, if applicable), they will be randomized to one of the three treatments 1:1:1 using a cluster-randomized design. That is, participants, not teeth, will be randomized, though multiple teeth per participant may be treated. Using the uniform distribution, the statistician will generate a random number sequence. We will use blocked randomization (blocks of six) to better ensure an even distribution across groups. Once group

Version date: 07/31/22

assignments have been made, the statistician will prepare numbered, opaque envelopes containing the random study arm assignments, which the investigators will use sequentially, as study participants accrue (i.e., the study identification number will match the number on the envelope).

7.0 STUDY AGENT ADMINISTRATION OR INTERVENTION AND TOXICITY MANAGEMENT PLAN

- 7.1 Treatment protocol after patients are randomized into one of three treatment groups:
 - 7.1.1 Fluoride varnish application (Control Group 1): Bulk saliva removed with saliva ejector. All teeth wiped dry with cotton gauze. One unit dose (0.4 ml) of fluoride varnish will be applied to all dentition then interproximal surfaces of all teeth will be flossed.
 - Professionally applied fluoride varnish has been shown to inhibit demineralization and enhance remineralization in early enamel caries.²² Current Caries Risk Assessment (CRA) protocol indicates fluoride varnish applications at 3-6 months intervals for high caries risk patients.^{4,5}
 - 7.1.2 SDF application with Super Floss *(Intervention Group 2)*: Petroleum jelly will be applied to lips and face to protect the skin from staining. Teeth will then be dried with an air-water syringe or wiped with gauze. Super Floss will be flossed through contact and left in place. The practitioner will apply SDF to the superfloss on the buccal or lingual aspect and then over the occlusal embrasure. Provider can visualize SDF being absorbed to the other end of the superfloss due to the blue tint of the SDF. Super floss will remain between the teeth, allowing the SDF to absorb, for one minute. Super floss is then removed and excess SDF removed with gauze or cotton roll. Fluoride varnish is applied over all teeth afterwards per high risk CRA protocol and current standard of care^{4,5}.
 - 7.1.3 SDF application without Super Floss (*Intervention Control Group 3*): Petroleum jelly will be applied to lips and face to protect the skin from staining. Teeth will then be dried with an air-water syringe or wiped with gauze, and teeth with interproximal caries isolated. SDF will be applied with microbrush over the occlusal embrasure of the interproximal surfaces of the target teeth. Excess SDF removed with gauze or

cotton roll. Fluoride varnish is applied over all teeth afterwards per high risk CRA protocol and current standard of care^{4,5}.

i. This control (secondary aim) is to determine if indirect/nearby SDF application can also be absorbed by the lesion and arrest caries.

7.2 Drug studies:

AGENT	DOSE	ROUTE	DAY	ReRx INTERVAL	NOTES
38% SDF	9.5mg/drop 1 drop = 25 μL	Topical	1	3 months, 6 months, 12 months	
5% Sodium fluoride varnish (2.26% [22,600ppm] fluoride)	22.6mg/mL 1 unit = 0.4mL	Topical	1	3 months, 6 months, 12 months	Fluoride varnish will be applied to each group.

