of the study, we will inflate the sample size by ~48% and recruit a total of 54-60 participants (108-120 caries). Sample size was calculated using PASS Software v.14.0 (Kayesville, UT).

This study is powered to detect an effect in a population of children who are predominantly non-white. Therefore, the sample size as calculated is likely to result in a sample size with reasonable power to detect an effect near the size outlined above, if perhaps slightly larger.

14.0 REGISTRATION GUIDELINE

- 14.1 Participants will be randomized as described in Section 6.3. Randomization envelopes will be available to the investigators, who need only select the next one in the series to accomplish randomization. No stratification parameters have been specified.
- 14.2 The forms and records needed for registration: Informed Consent; Assentfor Younger Subjects ; and Tracking Form.

Note: At the time of registration, two copies of a signed and dated patient Informed Consent form with Bill of Rights must be available (a copy for patient's dental chart; a copy for the subject/parent; and the original for the PI's file).

15.0 BIOHAZARD CONTAINMENT

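### Section 6.3 prints a single block size of six for an open-label, unstratified trial with sequential envelopes, so staff who follow earlier assignments could deduce about 20% of allocations in advance

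*Combined protocol and SAP*

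**What the plan says.** **Sequence.** Section 6.3 says of participants that "they will be randomized to one of the three treatments 1:1:1 using a cluster-randomized design", and makes clear that "participants, not teeth, will be randomized, though multiple teeth per participant may be treated". It continues: "We will use blocked randomization (blocks of six) to better ensure an even distribution across groups". Section 14.1 adds: "No stratification parameters have been specified". There is thus one sequence for the whole trial, with two places per arm in each block.

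**Concealment.** Under section 6.3, once eligibility and consent are complete, "the statistician will prepare numbered, opaque envelopes containing the random study arm assignments, which the investigators will use sequentially, as study participants accrue", and "the study identification number will match the number on the envelope". Section 14.1 says the envelopes are held by the investigators, "who need only select the next one in the series to accomplish randomization".

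**Who knows what.** Section 10.0 states that treating dentists and families are not blinded. Section 3.4 has the same residents and attendings of one programme trained to recognise eligible lesions, take consent and give the treatments.

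**Size.** Section 13.0 says the investigators had planned for 39 and "would now like to add 21 new participants for a total of 60 participants".

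The plan does not mention varying block sizes or keeping the block size from the investigators.

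**The concern.** Opaque envelopes hide what has not yet been opened. They do not stop anyone working out the next assignment from those already opened. Three features make that easy here: the block size is printed in the protocol, past assignments are visible because treatment is open, and study numbers equal envelope numbers, so numbers 6, 12, 18 and so on close a block.

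Randomizing after consent does not remove the problem, because a forced assignment is known before the next child is approached.

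What is at stake is selective enrolment. Whether to invite a child, how to rate behaviour (sections 5.1.4 and 5.2.6) and how to read a lesion at the border between categories 3 and 4 (sections 5.1.2 and 5.2.5) all call for judgement. Section 5.2.6 justifies its behaviour exclusion by reference to applying SDF, so that judgement could be coloured by knowing which arm comes next. The analysis relies on randomization for comparability. Section 13.0 examines confounders only if measured baseline variables differ, and behaviour rating is not among the descriptive factors in section 6.2.

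**Working it through.** The plan gives no figure for predictability, so there is none to reproduce. The calculation below rests on its stated design.

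**Inputs.** Three arms, 1:1:1, block of six (section 6.3), hence 2+2+2 per block and 6!/(2!·2!·2!) = 90 equally likely orderings. One sequence (sections 6.1 and 14.1). Total 60, of which 21 are added to 39 (section 13.0). Assumptions: every block has size six, and the observer knows all earlier assignments.

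**Certain allocations per block.**
- Positions 1 to 4: never certain.
- Position 5: certain only if the last two places belong to the same arm. Given the arm in one of them, 1 of the other 5 places holds its partner, so the probability is 1/5.
- Position 6: always certain.
- Expected number: 1/5 + 1 = 1.2 of 6 = 20%.

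**Over the trial.** 60 children are 10 blocks: 10 × 1.2 = 12.0. For the 39 originally planned, 6 complete blocks plus 3 places give 6 × 1.2 = 7.2 (18.5%).

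**The 21 added children.** The documents do not say whether a new list starts.
- New list: 21 = 3 blocks + 3 places, so 3 × 1.2 = 3.6.
- Old list continues: 39 = 6 × 6 + 3, so envelope 40 is position 4 of block 7. Finishing that block gives 1.2 and three further blocks give 3.6, together 4.8.

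**Best guess.** The best guess is the arm with most places left in the block. Its probability of being right at positions 1 to 6 is 1/3, 2/5, 1/2, 8/15, 3/5 and 1. The sum is 3.367, and 3.367/6 = 56.1%, against 33.3% by chance. For the 21 added children:
- New list: 3 × 3.367 + (1/3 + 2/5 + 1/2) = 11.3 correct guesses.
- Old list continues: (8/15 + 3/5 + 1) + 3 × 3.367 = 12.2.
- By chance: 21/3 = 7.

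**Effect of varying the block size.** Simulation of 2,000 sequences of 60, for an observer who knows the set of sizes and all past assignments:

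| Block sizes | Certain | Best guess right |
|---|---|---|
| 6 only | 20.0% | 56% |
| 3, 6 | 8.5% | 58% |
| 6, 9 | 5.0% | 54% |
| 3, 6, 9 | 3.7% | 55% |

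With sizes 3, 6 and 9, the 21 added children would include about 0.037 × 21 = 0.8 certain allocations.

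**Why guessing hardly changes.** Arm totals are equal at the end of every block, whatever its size. The arm used least so far is therefore always the best guess, and finding it needs no knowledge of block sizes. An observer using only that rule is right 56.1% of the time with blocks of six and 55.1% with sizes 3, 6 and 9.

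**The case against.** The plan has real safeguards. The statistician generates the sequence and prepares the envelopes. They are used in numerical order after eligibility and consent, so assignments cannot readily be exchanged once a child is in. Section 3.5 counts those asked, those who consent and those who drop out before or after randomization. Section 3.4 provides for training and standardization. Several residents and attendings take part, so each may see only part of the sequence. Blocking is also a sensible protection of balance in a trial of this size.

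Most of this stands and limits the weight of the point. It does not dispose of it. The counts in section 3.5 begin with children who are asked, so a child not approached, or approached later, leaves no trace there. One list with consecutive study numbers is easy to follow even when staff share the work.

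Two stronger readings are tempting, and neither is supported:
- A reader might infer that investigators do know one allocation in five, or that enrolment has been selective. The documents do not show that anyone tracked assignments. The 20% is what a person following every earlier assignment could deduce. No bias in the ICCMS endpoint has been estimated.
- A reader might infer that varying the block size would also cure the 11 to 12 correct guesses among the 21 added children. It would not, for the reason shown in the working.

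**Conclusion.** The point holds as an avoidable weakness in allocation concealment. It is a cheap improvement; the plan does not contradict itself here. With a single block size of six, 20% of allocations could be deduced with certainty: 12.0 of 60 overall, and 3.6 to 4.8 of the 21 added children.

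This rests on three assumptions: that every block has size six, which is the natural reading of the one size given; that the observer knows all earlier assignments; and that the 21 follow either a new list or a continuation from envelope 40. The documents do not say how many envelopes remain unopened, so how many children a change could still reach is unknown.

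**What to change.** For every unopened envelope, including those for the 21 added participants, the statistician should regenerate the sequence with block sizes chosen at random (for example 3, 6 and 9) and prepare new envelopes. Section 6.3 should say only that permuted blocks of randomly varying size are used. The sizes should be kept in a document held by the statistician, out of the protocol and away from the investigators.

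The amendment should describe the gain accurately: certain allocations fall from about 20% to about 4% even if the set of sizes is known, while best-guess accuracy stays at about 55%. Envelopes already opened cannot be repaired.

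The cost is one new list and one set of envelopes. Eligibility, treatment, endpoint and sample size do not change. Balance becomes slightly less exact if recruitment stops mid-block: arms can differ by up to 3 within an unfinished block of nine, against 2 within a block of six. Abandoning a partly used block of six at the changeover can itself leave a difference of up to 2.
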